4.4 Analysis Methods

4.4.1 General Statistical Considerations

Demographics, baseline characteristics, and the comparability of the PerClot and control group subjects will be assessed by tabulations of mean, median, range, standard deviation and analyses using t-tests of means or Wilcoxon tests for continuous factors. An appropriate test will be chosen by first testing for normality of two samples with Shapiro-Wilk test at alpha = 0.1. If normality is rejected for either sample, then the Wilcoxon test will be conducted. If normality is not rejected for either sample, then variances of two samples will be tested at alpha=0.1. If the equality of variance is rejected, then the t-test with Satterthwaite approximation will be conducted. If the equality of variance is not rejected, then a t-test will be conducted. For categorical factors, frequency, percent and Fisher's exact tests of proportions will be carried out. Achievement of hemostasis for all treated bleeding sites will be assessed by tabulating frequency of success as a percentage and analyses using Chi-square test.

4.4.2 Primary Efficacy

Primary efficacy will be measured by the proportion of subjects achieving hemostasis of the treated bleeding site at 7 minutes. The hemostasis status at 7 minutes will be used to define this endpoint. If a subject achieves hemostasis at an earlier time assessment (i.e., 5 minutes), but begins to re-bleed and the bleeding has not ceased by the 7 minute assessment, the subject will not be counted as achieving hemostasis at 7 minutes. The proportion of subjects achieving hemostasis will be summarized by treatment group. The difference between groups will be reported, along with the 95% confidence interval of the difference. Non-inferiority will be evaluated by comparing the upper bound of the confidence interval for the difference in treatment proportions ($P_{Control} - P_{PerClot}$) to the non-inferiority margin of 0.10. If the upper bound is found to be less than 0.1, the null hypothesis will be rejected and treatment will be considered non-inferior to control.

This analysis will be performed on the AT, ITT, and PP populations. The AT population will serve as the primary analysis population for the evaluation of the primary efficacy endpoint. Analyses based on the ITT and PP populations will be presented as supportive analyses. Additionally, the number of subjects in whom hemostasis is achieved at 7 minutes, but have a re-bleed during the 5 minute observation period following the 7 minute assessment will be summarized. A sensitivity analysis of the endpoint will be conducted where all subjects that achieved hemostasis at 7 minutes, but did not maintain it for the 5 minutes following the assessment or any time after the observation period, will be counted as 'failures' in the analysis.

Of note is that only subjects who have achieved hemostasis at 7 minutes will be observed for the additional 5 minutes. In cases where the wound has not achieved hemostasis at 7 minutes, it would be considered a failure and the surgeon is instructed to treat using alternate methods. Likewise, if the subject achieved hemostasis at 7 minutes and there is a breakthrough or re-bleeding at any point between the 7 and 12 minutes of assessment or any time after the observation period, the surgeon will immediately treat with alternate methods.

Success of the primary and secondary endpoints is determined by the treating physician's assessment. A supplementary secondary analysis of hemostasis endpoints will be performed based on the overall majority rule CEC assessment of hemostasis. The use of the CEC adjudications for analysis applies to all randomizations under protocol version 11 amendment 4 through version 11 amendment 7, as video capture was added to the protocol under version 11 amendment 4 and version 11 amendment 7 was the last amendment to require video capture. This analysis, which is based on CEC assessment of hemostasis rather than treating physician assessment, will exclude subjects randomized under a version of the protocol that does not require capture of video.

The CEC members assess a video of the bleeding region captured during the procedure. If the first two readers to assess a video agree about the outcome, a third reader is not required. A majority of two out of three members in agreement with each other is required to determine the overall CEC assessment. The table below indicates how the reader assessments are used to determine the overall CEC assessment of 7 and 5 minute hemostasis by a majority vote.

Table 4: Clinical Evaluation Committee Individual Assessments and Overall Endpoint Outcome

Clinical Evaluation Committee Individual Assessments			Overall CEC Outcome
Hemostasis	Hemostasis	3rd reader not required	Hemostasis
No Hemostasis	No Hemostasis	3rd reader not required	No Hemostasis

Not Evaluable	Not Evaluable	3rd reader not required	Indeterminate/missing
Hemostasis	No Hemostasis	Hemostasis	Hemostasis
Hemostasis	Not Evaluable	Hemostasis	Hemostasis
Hemostasis	No Hemostasis	No Hemostasis	No Hemostasis
No Hemostasis	Not Evaluable	No Hemostasis	No Hemostasis
Hemostasis	No Hemostasis	Not Evaluable	Indeterminate/missing
Hemostasis	Not Evaluable	Not Evaluable	Indeterminate/missing
No Hemostasis	Not Evaluable	Not Evaluable	Indeterminate/missing

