The Type I error, average sample size before adjusting for loss, and power were evaluated through a statistical simulation where binomial data was generated under several alternative hypotheses where the efficacy rate is equal between the two arms, but the efficacy rate is varied from 70% through 90%. The simulation results in the table below demonstrate that the Type I error is not inflated when the sample size is increased based on the pooled efficacy estimate and that power is maintained at 80% across all scenarios. The R code for the simulation is provided in Appendix B.

Table 3: Fixed versus BSSR Power and Sample Size Under Various Alternative Hypotheses

Alternative hypotheses (equal success rates)	Fixed Sample Size		Blinded Sample Size Reestimation (after 20% and 50% of subjects)	
	Sample Size (total after 5% loss)	Simulated Power	Final Sample Size (mean total after 5% loss)	Simulated Power
90%	308	81.1%	328	83.9%
85%	308	68.2%	414	80.1%
80%	308	59.0%	486	78.6%
75%	308	52.8%	508	73.9%
70%	308	48.3%	510	69.2%
Null hypothesis	Sample Size (total after 5% loss)	Type I Error	Final Sample Size (mean total after 5% loss)	Type I Error
80% (PerClot) vs 90% (Control)	308	2.3%	414	2.4%

If the observed efficacy rate is $\leq 60\%$ when the blinded sample size re-estimation is performed at 20% of enrollments or $\leq 64\%$ when the blinded sample size re-estimation is performed at 50% of enrollments, the DSMB will evaluate the overall study data and make a recommendation regarding whether to stop the study prematurely due to an unacceptable efficacy rate. The boundaries of 60% and 64% were selected based on those observed rates have $<5\%$ chance of being observed if the population efficacy rate is 70% or higher.

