In the event that the DSMB recommends that the study be stopped due to low efficacy at an interim analysis, the two study arms will be compared based on the available data in the As Treated population. There is the possibility that a low pooled success rate is due primarily to one of the two study arms. If the PerClot success rate is sufficiently higher than the control success rate that the non-inferiority Z-value would cross a group sequential boundary based on a Lan-DeMets alpha-spending function with the information fraction based on the planned sample size of 324 (boundaries are $Z=4.42$ at 20% and $Z=2.80$ at 50%), then the statistical criteria for rejecting the null hypothesis will be met based on the available data. However, as the data may not be sufficient to adequately assess the overall performance of PerClot in this scenario, discussion with FDA is warranted prior to closure of the trial.

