4.4.4 Safety Analyses

Safety data will be summarized by incidence of each adverse event type along with 95% exact confidence intervals. Adverse event rates will be reported as the proportion of subjects who experience an event and the total number of each event type occurring.

Adverse events will be summarized by relatedness, seriousness, and severity. The comparison of safety between treatment arms will be based on Fisher's exact tests for the proportion of subjects with serious device-related adverse events, unanticipated adverse device effects, and frequent adverse events ($\geq 5\%$ overall incidence) in the two treatment groups.

The other following safety endpoints will also be summarized using descriptive statistics:

- Total operative time;
- Hemostasis at 5 to 7 minutes;
- Hemostasis maintenance;
- Total intraoperative estimated blood loss;
- Alternative means required to achieve hemostasis (where applicable);
- Units of blood transfused intraoperatively and postoperatively (where applicable);
- Incidence of reoperation;
- Total hospitalization time;
- Incidence of procedure complications;
- Incidence of adverse events through final follow-up, including, but not limited to:
 - Adhesions or fibrosis;
 - Anaphylaxis;
 - Blockage of the bladder or ureteral lumen;
 - Blockage of the bypass system;
 - Cancer recurrence and/or progression;
 - Compromised attachment of prosthetic devices to bone or tissue;
 - Death;
 - Embolism;
 - Failure of deep or superficial wound healing;
 - Failure to obtain hemostasis;
 - Fever;
 - Hemorrhage;
 - Infection;
 - Peri-operative hyperglycemia;
 - Exacerbation of surgical procedure-associated adverse events;
 - Swelling and compression of pressure-sensitive tissues and structures;
 - Thromboembolism;
 - Thrombosis; and
 - Toxicity.

Safety analyses are descriptive in nature. There are no formal hypothesis tests associated with these outcomes. All safety analyses will be performed on the ITT population.

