4.8 Missing Data

Every effort will be made to collect all data points in the study. The amount of missing data will be minimized by appropriate management of the clinical study, training of participating investigators and study coordinators, and sufficient monitoring of study sites. As the primary efficacy endpoint data are collected intraoperatively, missing data is expected to be minimal, and subject withdrawal and loss to follow-up during the follow-up period is not expected to impact the efficacy analysis.

To assess the impact of missing data on the primary endpoint, a sensitivity analysis will be conducted. The primary endpoint analysis will be repeated under two scenarios: one in which all missing endpoints are assumed to be successes for the PerClot group and failures for the control group, and another in which all missing endpoints are assumed to be failures for the PerClot group and successes for the control group. If these scenarios do not impact the conclusion of the analysis, then the impact of missing data will be considered inconsequential. The reason for any significant differences between scenarios will be investigated and reported.

5 Analysis Software

All analyses will be performed using SAS statistical software (SAS Institute; Cary, NC) or a comparable statistical software.

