Appendix A – Sample Size Calculation with PASS

PASS sample size calculation software (version 13) was used to calculate the power for the primary endpoint (shown below).

Analysis of Non-Inferiority Tests of Two Independent Proportions

Numeric Results for Non-Inferiority Tests Based on the Difference: P1 - P2
H0: P1 - P2 ≤ D0. H1: P1 - P2 = D1 > D0. Test Statistic: Score test (Farrington & Manning)

Diff Power ha	Diff N1 Alpha	Target N2	Actual N	Ref.	P1 H0	P1 H1	NI		
				P2	P1.0	P1.1	D0	D1	Alp
0.79885	154	154	308	0.9000	0.8000	0.9000	-		
0.1000	0.0000	0.0250							

Note: Direct Binomial distribution calculations for alpha and power were only used when both N1 and N2 were less than 100. In all other cases, Normal approximation was used.

References

Farrington, C. P. and Manning, G. 1990. 'Test Statistics and Sample Size Formulae for Comparative Binomial Trials with Null Hypothesis of Non-Zero Risk Difference or Non-Unity Relative Risk.' Statistics in Medicine, Vol. 9, pages 1447-1454.

Fleiss, J. L., Levin, B., Paik, M.C. 2003. Statistical Methods for Rates and Proportions. Third Edition. John Wiley & Sons. New York.

Gart, John J. and Nam, Jun-mo. 1988. 'Approximate Interval Estimation of the Ratio in Binomial Parameters: A Review and Corrections for Skewness.' Biometrics, Volume 44, Issue 2, 323-338.

Gart, John J. and Nam, Jun-mo. 1990. 'Approximate Interval Estimation of the Difference in Binomial Parameters: Correction for Skewness and Extension to Multiple Tables.' Biometrics, Volume 46, Issue 3, 637-643.

Lachin, John M. 2000. Biostatistical Methods. John Wiley & Sons. New York.

Miettinen, O.S. and Nurminen, M. 1985. 'Comparative analysis of two rates.' Statistics in Medicine 4: 213-226.

Report Definitions

Power is the probability of rejecting a false null hypothesis.

N1 and N2 are the number of items sampled from each population.

N is the total sample size, N1 + N2.

P2 is the proportion for Group 2. This is the standard, reference, or control group.

P1 is the treatment or experimental group proportion. P1.0 is the smallest treatment-group response rate that

still yields a non-inferiority conclusion. P1.1 is the proportion for Group 1 at which power and

sample

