Appendix B – Blinded Sample Size Re-estimation Simulation

```

library(gsDesign) # for nBinomial Farrington-Manning sample size

set.seed(843112)

ssFMnoninf <- function(pA=0.9, pB=0.9, delta=-0.10, alpha=0.025, beta=0.20)
{
  out <- ceiling(nBinomial(p1=pA, p2=pB, alpha=alpha, beta=beta, delta=delta,
  ratio=1, sided=1)/2)
}

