# when !interim2GEinit
# or simulate all n.tointerim2 at once
n.tointerim2[!interim2GEinit] <- n.interim2[!interim2GEinit] - n.interim1
a.interim2[!interim2GEinit] <- a.interim1[!interim2GEinit] +
rbinom(n=n.interim2LTinit, size=n.tointerim2[!interim2GEinit], prob=pA)
b.interim2[!interim2GEinit] <- b.interim1[!interim2GEinit] +
rbinom(n=n.interim2LTinit, size=n.tointerim2[!interim2GEinit], prob=pB)

pooled.estimate.interim2 <- (a.interim2 + b.interim2) / (2*n.interim2)
sample.sizes.interim2 <- ssFMnoninfeq(pooled.estimate.interim2, tol)
n.total.interim2 <- pmin(n.interim2max, pmax(n.total.interim1, sample.sizes.interim2))

prob.ss.10pct.interim2 <- sum(abs(n.total.interim2 - correct.ss)/correct.ss < 0.1)/n.sim
prob.ss.5pct.interim2 <- sum(abs(n.total.interim2 - correct.ss)/correct.ss < 0.05)/n.sim

n.tofinal <- n.total.interim2 - n.interim2

a.final <- a.interim2 + rbinom(n=n.sim, size=n.tofinal, prob=pA)
b.final <- b.interim2 + rbinom(n=n.sim, size=n.tofinal, prob=pB)

n.final <- n.total.interim2

pvals <- 1-pnorm(testBinomial(a.final, b.final, n.final, n.final, delta0=-0.1)) # one-sided
by default

n.tofix[!interim2GEinit] <- n.init - n.interim2[!interim2GEinit]
a.fix[!interim2GEinit] <- a.interim2[!interim2GEinit] + rbinom(n=n.interim2LTinit,
size=n.tofix[!interim2GEinit], prob=pA)
b.fix[!interim2GEinit] <- b.interim2[!interim2GEinit] + rbinom(n=n.interim2LTinit,
size=n.tofix[!interim2GEinit], prob=pB)
n.fix[!interim2GEinit] <- n.interim2[!interim2GEinit] + n.tofix[!interim2GEinit]

pvalsfix <- 1-pnorm(testBinomial(a.fix, b.fix, n.fix, n.fix, delta0=-0.1)) # one-sided by
default

return(list(n.interim1=n.interim1, n.interim2.mean=mean(n.interim2),
fix.power=sum(pvalsfix<alphaFIX)/n.sim,
bssr.power=sum(pvals<alphaBSS)/n.sim,
ss.mean=mean(n.final), ss.sd=sd(n.final),
ss.min=min(n.final), ss.max=max(n.final),
ss.probmax=sum(n.final==n.interim2max)/n.sim,
ss.wi10pct=prob.ss.10pct.interim2, ss.wi5pct=prob.ss.5pct.interim2))

}

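### Does the unnamed confidence interval method in SAP 4.4.2 and 4.4.3 leave the non-inferiority verdict open?

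*SAP*

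**What the plan says.** The success rule appears in SAP 4.2.1 and 4.2.3 and in Protocol 6.6.7: the upper bound of a one-sided 97.5% interval for control minus PerClot must be below 0.10. SAP 4.4.2 states it through a two-sided interval, which has the same upper bound: "The difference between groups will be reported, along with the 95% confidence interval of the difference". SAP 4.4.3 uses the same sentence for the secondary endpoint. None of these sections names a method.

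The method is named where the design is worked out. SAP 4.2.1.1 bases its power statement on the one-sided 97.5% interval and refers to Appendix A, whose PASS output reads "Test Statistic: Score test (Farrington & Manning". Appendix B loads its package with the line "library(gsDesign) # for nBinomial Farrington-Manning sample size" and obtains each final p-value from "testBinomial(a.final, b.final, n.final, n.final, delta0=-0.1". On Table 3, SAP 4.2.1.2 says: "The simulation results in the table below demonstrate that the Type I error is not inflated when the sample size is increased".

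Three other places matter. For adverse events the SAP does name its interval: "Safety data will be summarized by incidence of each adverse event type along with 95% exact confidence intervals". Section 5 leaves the software open: "All analyses will be performed using SAS statistical software (SAS Institute; Cary, NC) or a comparable statistical software". If the DSMB recommends stopping for low efficacy, SAP 4.2.1.2 asks whether the "non-inferiority Z-value would cross a group sequential boundary based on a Lan-DeMets alpha-spending function", again without defining the statistic.

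**The concern.** The bound is the whole success criterion, and different intervals can give different verdicts on the same data. The sizing ran in PASS and the simulation in R, while the analysis will run in SAS or similar, so nothing carries the test across mechanically. A programmer with only 4.4.2 in hand could compute a Wald interval and claim compliance. Near the planned rates the Wald bound is the more lenient: at 154 per arm and 90% success in both arms, practically every disagreement with the score test favours PerClot. The SAP's claim that Type I error is not inflated was shown for the score test. If the method were picked after the arms had been compared, the pick could settle a close result.

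**Working it through.** **Inputs.** One-sided alpha 0.025, margin 0.10, 90% success in both arms, 154 per arm (SAP 4.2.1.1); re-estimation limits of 154 and 255 per arm, with coded rates 0.901 for power and 0.799 versus 0.900 for error (Appendix B).

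**1. The plan's own figure.** Under the null constraint, the restricted estimates at 90% versus 90% are 0.8313 (PerClot) and 0.9313 (control).

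- SE under the null = √[(0.8313×0.1687 + 0.9313×0.0687)/154] = 0.0364
- SE under the alternative = √[2×0.90×0.10/154] = 0.0342
- Power = Φ[(0.10 − 1.96×0.0364)/0.0342] = Φ(0.8375) = 0.7988, against 0.79885 in Appendix A

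A Wald-type formula would have asked for (1.960 + 0.842)² × 0.18/0.10² = 141.3, so 142 per arm. The planned 154 therefore comes from the score test.

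**2. Table 3.** Re-running the re-estimation rule with the score test, at the coded rates:

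| Quantity | SAP Table 3 | Recomputed |
|---|---|---|
| Fixed power, 90% | 81.1% | 81.2% |
| Re-estimation power, 90% | 83.9% | 83.9% |
| Mean total N, 90% | 328 | 328 |
| Error, fixed | 2.3% | 2.33% |
| Error, re-estimation | 2.4% | 2.36% |

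**3. What a Wald interval would change.** Exact one-sided error, summing binomial probabilities over all outcomes:

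| PerClot vs control | n per arm | Score | Wald |
|---|---|---|---|
| 80% vs 90% | 154 | 2.47% | 2.78% |
| 80% vs 90% | 162 | 2.47% | 2.68% |
| 80% vs 90% | 207 | 2.46% | 2.63% |
| 80% vs 90% | 255 | 2.49% | 2.64% |
| 75% vs 85% | 154 | 2.48% | 2.59% |
| 70% vs 80% | 154 | 2.55% | 2.55% |
| 60% vs 70% | 154 | 2.58% | 2.51% |
| 85% vs 95% | 154 | 2.35% | 3.10% |

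At the SAP's own null of 80% versus 90%, the excess is 2.78 − 2.47 = 0.31 points at 154 per arm and 2.64 − 2.49 = 0.15 points at 255. With re-estimation, score and Wald give 2.50% and 2.78% there, and 2.37% and 3.13% at 85% versus 95%.

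**4. Other intervals.** At 154 per arm, with error at 80% versus 90% and power at 90% versus 90%:

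| Method | Error | Power |
|---|---|---|
| Score | 2.47% | 80.9% |
| Miettinen-Nurminen | 2.36% | 80.8% |
| Newcombe | 2.55% | 81.3% |
| Agresti-Caffo | 2.76% | 82.8% |
| Wald | 2.78% | 83.5% |
| Wald, continuity-corrected | 1.82% | 78.2% |

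The stated operating characteristics are therefore not peculiar to one method.

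**5. How often the verdict differs.** At 90% versus 90%, score and Wald disagree in 2.7% of trials at 154 per arm, 1.6% at 162, 1.2% at 207 and 0.5% at 255. One such case is control 141/154 and PerClot 136/154: the difference is 0.0325 with Wald SE 0.0342, so the Wald bound is 0.0325 + 1.96×0.0342 = 0.0996 (success). The score bound is 0.1027 (failure).

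**6. The interim Z.** With 32 per arm, PerClot 26 and control 12 successes (pooled 38/64 = 59%) give Z = 4.89 by Wald and 4.39 by score, on either side of 4.42. The chance of a disagreement at that look, with pooled success at or below 60%, is about 5×10⁻¹⁴ if both rates are 90% and 2.6×10⁻⁵ if both are 70%. It becomes material only with a very large true difference (11% at 80% versus 40%).

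**The case for a change.** The strongest case is that the one number deciding the trial should not rest on inference from an appendix. SAP 4.2.1.1 cites Appendix A in a sizing section, which does not prescribe the analysis. The SAP takes the trouble to name exact intervals for adverse events and a chain of pre-tests for baseline comparisons (4.4.1). The Chi-square test that 4.4.1 mentions for hemostasis cannot supply a non-inferiority bound. Naming the score interval would take a sentence in each place and cost no patients and no power that the SAP claims.

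A control rate above 90% is also possible. Protocol 3.3.1 reports hemostasis by 3 minutes in every Arista patient, while Protocol 3.3.3 reports 80.0% at 5 minutes in 15 Arista patients. Wald error keeps growing towards the ceiling: at 154 per arm it is 3.10% with control at 95% and about 4.5% at 99%.

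What stands is that the detail is missing, that writing it down would be tidy, and that Wald is a poor choice at very high success rates. What does not stand is the step from silence to permission. Nothing in either document points to Wald, and everything in the design points to the score test. A statistician who reads 4.2.1.1 and the appendices has one natural choice, and choosing Wald would mean setting aside the test behind the SAP's own error claim. The interim example also needs a pooled rate at or below 60%, a DSMB recommendation to stop and PerClot about 44 points ahead, and the SAP calls for discussion with FDA before closure.

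A stratified sensitivity analysis would add little. Under assumed stratum rates it moves power by −0.2 to +0.5 points at 85 to 90% success, and SAP 4.6 and 4.7 already provide adjusted and by-area results.

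**Conclusion.** No change is needed. The plan states no wrong rule: it omits a method name that its own appendices supply, and analysts would sensibly fill the gap with the Farrington-Manning score interval, under which the stated power and error reproduce. If someone did use Wald, the cost at the SAP's null of 80% versus 90% would be 0.15 to 0.31 points of one-sided error, shrinking as the sample grows. At control rates of 80 to 85% error would be about 2.5 to 2.6%, close to the score test's own. The conclusion would remain essentially sound.

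This rests on two assumptions: that the analyst follows the test in Appendices A and B, or else that control success is near or below the planned 90%. With control at 95% or more the Wald excess is no longer trivial, but that combines a rate outside the SAP's scenarios with a method that the SAP nowhere uses.

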A strong linear correlation was found between mass of fluid collected and calculated blood volume based on hemoglobin concentration measurement. The mass of fluid and calculated blood volume collected over 30 seconds have a significant effect on the achievement of hemostasis by 5 minutes. This suggests that an objective measure, such as fluid mass loss, can be accurately applied when assessing the severity of bleeding for an injury. Further, the efficacy of both PerClot and Surgicel has been determined for a range of bleeding severities assessed using this method.

There were no strong relationships between bleeding severity and the amount of PerClot or Surgicel applied.

3.2.15 GLP Evaluation of the Safety of PerClot on Cranial Bone Healing in a Rabbit Model

A GLP preclinical evaluation was performed to assess the safety of PerClot on cranial bone healing in a rabbit model.

The objectives of this study were as follows:

- Evaluate the safety of PerClot compared to clinical available hemostatic agents (i.e. bone wax),
 - Evaluate bone healing and regrowth using histology; and
 - Compare effect(s) of PerClot on bone healing and regrowth to effect(s) of bone wax on bone healing and regrowth.

A total of 34 rabbits were utilized for evaluation in this study. Each animal underwent a surgical procedure to create two circular cranial injuries (7mm diameter) at the mid-point of each parietal bone through the full thickness of the skull. A test article, control article (bone wax) or no-treatment control was applied to each injury. At 0 (acute), 42 (+3) and 70 (+3) days post-operation, designated animals were euthanized and injury sites were excised and fixed in 10% neutral buffered formalin. Fixed tissues underwent histopathological processing and evaluation.

Microscopic evaluation of cranial injury sites implanted for 0 (acute), 42 (+3) and 70 (+3) days (actual duration 0, 42, 47, 48, 70 or 71 days) revealed the following:

- There was abundant residual bone wax present at both time points, while very little of the test article, PerClot, was present at either day 42 or day 70, with most sites having no residual material at either time point.
- Both residual bone wax and PerClot were associated with a foreign body inflammatory response. This response was greater overall for the bone wax.

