*For oncology subjects only.

3 Randomization and Blinding

The randomization schedule will be stratified by site, therapeutic area, and bleeding severity score, and will be generated using random permuted blocks of size two and four. Subjects will be randomized on a 1:1 allocation to either PerClot or the control group. A subject may agree to participate and sign the ICF, but ultimately not be enrolled due to failure to meet the intraoperative eligibility criteria. Only subjects meeting the intraoperative eligibility criteria will be randomized and enrolled.

This will be a single-blinded trial. The subjects will be blinded as to the hemostatic treatment received. Unblinding will be permitted after a subject has completed his or her 6 week follow-up visit evaluations.

4 Statistical Methods

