4.2.1.1 Sample Size Justification

The sample size was calculated based on the following assumptions:

- One-sided alpha = 0.025;
- Minimum 80% power;
- Non-inferiority margin $\delta = 0.10$;
- Expected 7 minute hemostatic success rate in the PerClot group is 90%; and
- Expected 7 minute hemostatic success rate in the control group is 90%.
- Randomization allocation of 1:1

A sample size of 154 subjects in each group will provide approximately 80% power to reject the hypothesis of the inferiority of PerClot to the composite control by a 10% margin, using a one-sided 97.5% confidence interval (see Appendix A). As the primary endpoint data is collected intraoperatively, no adjustment is made for attrition; however, the sample size was increased to account for the possibility of up to 5% loss within either group due to technical failures (i.e., contraindications, misdiagnosis, or intraoperative death prior to treatment, etc.), and subjects not treated according to randomization assignment, resulting in a sample size of 162 per arm to ensure >80% power. Thus, a total of 324 subjects is the planned sample size to enroll, assuming an efficacy rate of 90%.

A non-inferiority margin of 10% is consistent with the margins used in other controlled clinical trials involving hemostatic agents.^{2, 3} A non-inferiority margin $\delta = 0.10$ was chosen for this study because excluding a 10% difference between the treatments would be supportive of non-inferior performance of PerClot compared to the control.

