4.2.2 Secondary Efficacy

The secondary efficacy objective will be evaluated at 5 minutes in a manner similar to the primary efficacy analysis. The secondary hypothesis for this clinical investigation is that the proportion of subjects achieving hemostasis of the treated bleeding site at 5 minutes in the PerClot group is non-inferior to the proportion of subjects achieving hemostasis of the treated bleeding site at each evaluation time point in the control group.

$$H_0: P_{t,PerClot} < P_{t,Control} - \delta$$
$$H_a: P_{t,PerClot} \geq P_{t,Control} - \delta$$

where $P_{PerClot}$ is the proportion of PerClot subjects achieving hemostasis of the treated bleeding site at time point t , $P_{t,Control}$ is the proportion of control subjects achieving hemostasis of the treated bleeding site at time point t , and δ is the non-inferiority margin, with $\delta = 0.10$.

In other words, the null hypotheses are that the proportion of PerClot subjects achieving hemostasis of the treated bleeding site at each evaluation time point will be inferior to the proportion of control subjects achieving hemostasis of the treated bleeding site at each evaluation time point. The alternative hypotheses are that the proportion of PerClot subjects achieving hemostasis of the treated bleeding site at each evaluation time point will be equal to or greater than, or not inferior to, the proportion of control subjects achieving hemostasis of the treated bleeding site at each evaluation time point. Each null hypothesis will be rejected in favor of the corresponding alternative hypothesis if the upper bound of the 97.5% one-sided confidence interval for the difference in treatment proportions ($P_{t,Control} - P_{t,PerClot}$) is less than 0.10.

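### The deciding 7- and 5-minute non-inferiority intervals leave out the randomization strata, so if those strata are prognostic the test is slightly conservative and forgoes a little power

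*SAP*

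**What the plan says.** SAP 3 sets the allocation: "The randomization schedule will be stratified by site, therapeutic area, and bleeding severity score, and will be generated using random permuted blocks" of two and four. Protocol 6.6.8 agrees.

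For the primary endpoint, SAP 4.4.2 states: "The proportion of subjects achieving hemostasis will be summarized by treatment group". It then gives the decision rule: "Non-inferiority will be evaluated by comparing the upper bound of the confidence interval for the difference in treatment proportions" with the 0.10 margin. No stratum weights, adjusted estimator or interval method is named. SAP 4.2.3 makes that comparison, in the As Treated population, the sole criterion of trial success. For the secondary endpoint, SAP 4.2.2 states: "The secondary efficacy objective will be evaluated at 5 minutes in a manner similar to the primary efficacy analysis". SAP 4.4.3 repeats the primary form.

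The sizing assumptions in SAP 4.2.1.1 include "One-sided alpha = 0.025" and "Minimum 80% power". Appendix A uses an unstratified Farrington-Manning score test, and the re-estimation code in Appendix B uses the matching unstratified sample size and test functions.

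The strata do appear elsewhere:
- SAP 4.5 reports differences with intervals by bleeding severity score and tests the interaction, described as descriptive.
- SAP 4.6 gives an adjusted difference with a 95% interval from a multivariable logistic model. Therapeutic area and continuous initial bleeding severity are among the candidates, kept at the 0.1 level.
- SAP 4.7 adjusts for site or therapeutic area if a poolability test reaches 0.15.

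None of these decides success.

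**The concern.** Stratified randomization balances the arms within each stratum. If success rates differ between strata, that balance removes part of the chance variation in the difference between arms. The crude variance still counts it, so the crude interval is wider than the design requires and the true one-sided error falls below nominal.

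There is some reason to expect prognostic strata. The pig-liver comparison in Protocol 3.2.14 reports: "The mass of fluid and calculated blood volume collected over 30 seconds have a significant effect on the achievement of hemostasis by 5 minutes". Eligible bleeding flux runs from above 0.000040 to 0.013 (Protocol 6.3.2), about a 325-fold range (0.013 / 0.000040), split into only two scores.

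The adjusted analyses in the plan do not take the place of an analysis by stratum. The model in SAP 4.6 selects terms by significance, and its candidates include quantities measured after device application, such as drainage volume and rinse volume. The adjustment in SAP 4.7 is conditional and omits severity. What is at stake is efficiency. The direction of error is towards failing to show non-inferiority, not towards claiming it falsely.

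**Working it through.** **1. Reproduce the plan's power.** Inputs from SAP 4.2.1.1 and Appendix A: 90% in both arms, margin 0.10, one-sided 0.025, 154 per arm, score test.

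- Restricted maximum-likelihood rates under a difference of -0.10: 0.8313 and 0.9313.
- Null SE = sqrt[(0.8313 × 0.1687 + 0.9313 × 0.0687) / 154] = 0.0364.
- SE under equal rates = sqrt(2 × 0.9 × 0.1 / 154) = 0.0342.
- Power = Φ[(0.10 - 1.96 × 0.0364) / 0.0342] = Φ(0.838). Unrounded this is 0.79885, the Appendix A figure. With 162 per arm it is 81.9%.

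SAP Table 2 also reproduces, from 308 (using the 0.901 rate in Appendix B) to 510 at 80%. The planned 80% therefore belongs to the unstratified test.

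**2. Variance that stratification removes.** With stratum shares w and rates p, the ratio of within-stratum to marginal variance is R = Σ w p(1-p) / [p̄(1-p̄)]. Stratum rates are assumed; six equal strata (three areas by two scores).

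- All 90%: R = 1.
- 80% to 98%, mean 90%: R = 0.963.
- 76% to 99%, mean 90%: R = 0.935. The 95% half-width falls from 6.70 to 6.48 points.
- 98/96/94/90/84/72: mean 89%, R = 0.0901 / 0.0979 = 0.92.
- 99.5/98/97/92/82/60: mean 88.1%, R = 0.0858 / 0.1050 = 0.82. Nothing in the documents supports a spread this wide.

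**3. Power and error by simulation.** Crude score test against stratified score test with Mantel-Haenszel weights, six near-equal strata, 1:1 within stratum, 60,000 trials per scenario where stated. Error is at a true difference of -0.10 in every stratum.

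| Assumed stratum rates | Evaluable n | Crude power | Stratified power | Difference | Crude error |
|---|---|---|---|---|---|
| All 90% | 308 | 80.9% | 81.5% | 0.6 | 2.6% |
| 81% to 97% | 308 | 81.5% | 81.9% | 0.4 | 2.3% |
| 98/96/94/90/84/72 | 308 | 79.4% | 80.4% | 1.0 | 2.2% |
| 99.5/98/97/92/82/60 | 308 | 78.0% | 80.7% | 2.7 | 1.7% |
| 97/93/90/86/78/66 (mean 85%) | 414 | 81.7% | 83.1% | 1.4 | not quoted |

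A repeat of the last row put the gain nearer 1.3 points. The stratified test's error was 2.4% to 2.7%.

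**4. Reading the table.** The first row has no stratum effect, so its 0.6-point gap is not a gain from stratifying. Measured from that row, the gain at 308 runs from nil (0.4 - 0.6) to about 2 points (2.7 - 0.6 = 2.1). The crude figures of 79.4% and 78.0% lie below 80% because the mean rates are 89% and 88.1%. At those rates SAP Table 2 would raise the sample to 332 and about 352.

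**5. Keep the statistic the same when comparing.** With no spread, crude score power was 80.7% and Mantel-Haenszel (Sato variance) 83.3% in a 200,000-trial run. That gap is a change of statistic. Crude Wald against Mantel-Haenszel gave 83.4% vs 83.3% (no spread), 84.3% vs 85.0% (80% to 98%) and 84.6% vs 85.9% (76% to 99%).

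The 5-minute effect cannot be sized because the plan assumes no 5-minute rate.

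**The case against.** The case for leaving the test alone is substantial, and most of it stands.

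- **Planned power is met.** A reader might infer that the trial is underpowered. Step 1 shows otherwise.
- **Re-estimation covers a lower success rate.** A reader might take the fixed-sample 68.2% at an 85% rate in SAP Table 3 as the power that stratification must rescue. The same row shows re-estimation to 414 and 80.1%.
- **The strata are not ignored.** SAP 4.5 and 4.6 use severity, and 4.6 can yield an adjusted difference without any poolability trigger. These analyses are supportive, so this narrows the point without answering it.
- **Evidence that the strata are prognostic is thin.** The pig study has a 5-minute outcome and covers a wide severity range. It also reports at least 90% success for both hemostats when 1.0 to 10.0 g was collected. The trial enrols only scores 1 and 2, and SAP 4.7 expects therapeutic areas to be poolable. Nothing quantifies a 7-minute difference between strata.
- **The crude test errs on the safe side.** Accepting slight conservatism in a non-inferiority trial is defensible.
- **The change is more than one sentence.** SAP Tables 2 and 3 and Appendix B describe the unstratified test.

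What remains is that recorded strata, fixed before treatment, are absent from the one analysis that decides success, and using them costs little.

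**Conclusion.** The point holds as a modest efficiency improvement. The deciding 7- and 5-minute intervals omit the randomization strata. If those strata are prognostic, the crude test runs at about 1.7% to 2.3% one-sided error and forgoes roughly 0.5 to 3 power points, the upper end only under an extreme spread. Part of that range appears even without stratum differences. At a pooled 85% rate after re-estimation to 414, the gain is about 1.3 to 1.4 points. If the strata are not prognostic there is essentially no difference.

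These figures rest on assumed stratum rates and near-equal strata. The documents do not support reading this as a shortfall against plan, an invalid test or a risk of false success. Nor should the variance ratios (8% and 18% reductions in the two widest spreads) be read as sample size thrown away: like for like, the power gained is small.

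**What to change.** Before outcomes are compared by arm, amend SAP 4.4.2 and 4.4.3, with matching wording in 4.2.1 to 4.2.3 and Protocol 6.6.7:

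- Make the deciding 7- and 5-minute interval a stratified score (Miettinen-Nurminen) interval for the common risk difference, with Mantel-Haenszel weights over the therapeutic area by severity score strata as randomized.
- Leave site out. About 13 to 40 subjects per site, crossed with area and severity, would give very sparse cells.
- Keep the crude interval as a named sensitivity analysis.

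Leave the margin, sample size and re-estimation table unchanged. Add a note that SAP Tables 2 and 3 and Appendix B describe the unstratified test and so are slightly conservative for the stratified one.

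The cost is document wording and routine programming, since the strata are already recorded. The change also settles the unnamed interval method in 4.4.2: with no spread, crude Wald and crude score power differed by 2.7 points (83.6% vs 80.9%). If the sponsor prefers the crude test, the minimum is to name its interval method, say that its conservatism is accepted, and add the stratified interval as a named sensitivity analysis.
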